### **Participant Duration:**

The baseline (Attack) visit will take place at the earliest timepoint possible following hospital admission. A follow up visit will be arranged, approximately 2 weeks after hospital discharge. A third telephone follow up visit will be arranged approximately 4 weeks after hospital discharge.

Study participants will be participating in the study from the time of consent (earliest timepoint possible following hospital admission) up to approximately four weeks following hospital discharge. This could be from 4-12 weeks depending on the length of hospital stay. The maximum length of participation in the study is 12 weeks per participant.

## **End of the Trial**

The end of the study will be the last visit of the last participant.

## **SELECTION AND WITHDRAWAL OF PARTICIPANTS**

### **Recruitment**

Page 16 of 35

Phenotyping Asthma Exacerbations: A Longitudinal Cohort Study 3 (APEX 3)  
Protocol: Final Version 1.0      10.11.2021      IRAS: 304615

This protocol is confidential and the property of the University of Nottingham. No part of it may be transmitted, reproduced, published, or used by others persons without prior written authorisation from the University of Nottingham

Participants will be identified and recruited from admission units or inpatient wards at the Nottingham City Hospital, or the emergency department at Queens Medical Centre. The initial approach will be from a member of the patient's usual care team (which may include the investigator).

The investigator or their nominee, e.g., from the research team or a member of the participant's usual care team, will inform the participant or their nominated representative (other individual or other body with appropriate jurisdiction), of all aspects pertaining to participation in the study.

It will be explained to the potential participant that entry into the trial is entirely voluntary and that their treatment and care will not be affected by their decision. It will also be explained that they can withdraw at any time, but attempts will be made to avoid this occurrence. In the event of their withdrawal, it will be explained that their data collected so far cannot be erased and we will seek consent to use the data in the final analyses where appropriate.

## **Eligibility criteria**

### **Inclusion Criteria**

- The ability to give fully informed consent
- Male or female aged  $\geq 18$  years of age.
- Admission with a suspected acute asthma attack.
- Able (in the investigator's opinion) and willing to comply with clinical investigation requirements.

### **Exclusion Criteria**

- Other clinically significant respiratory diseases including predominant Chronic Obstructive Pulmonary Disease (COPD) and bronchiectasis.
- Any other clinically significant medical disease or uncontrolled concomitant disease that is likely, in the investigator's opinion, to impact the ability to participate in the study or the study results.
- Pregnant women, lactating women or women who are planning to become pregnant.
- Investigator determined apparent other cause for admission.
- Acute COVID infection.
- Non-English-speaking participants who are unable to comprehend the reasons for the study due to limitations in understanding the English language.

### **Expected duration of participant participation**

Study participants will be participating in the study for 4-12 weeks depending on the length of hospital stay. The maximum length of participation in the study is 12 weeks per participant.

### **Removal of participants from therapy or assessments/Participant Withdrawal**

There are no plans to specifically withdraw participants from the study, unless they withdraw consent or cannot be contacted by the research team, despite several attempts.

Participants may be withdrawn from the trial either at their own request or at the discretion of the Investigator. The participants will be made aware that this will not affect their future care. Participants will be made aware (via the information sheet and consent form) that should they withdraw the data collected to date cannot be erased and may still be used in the final analysis.

## **Informed consent**

All participants will provide written informed consent. The Informed Consent Form will be signed and dated by the participant before they enter the trial. The Investigator will explain the details of the trial and provide a Participant Information Sheet, ensuring that the participant has sufficient time to consider participating or not. The Investigator will answer any questions that the participant has concerning study participation.

Informed consent will be collected from each participant before they undergo any interventions (including physical examination and history taking) related to the study. One copy of this will be kept by the participant, one will be kept by the Investigator, and a third will be retained in the patient's hospital records.

Should there be any subsequent amendment to the final protocol, which might affect a participant's participation in the trial, continuing consent will be obtained using an amended Consent form which will be signed by the participant.

Loss of capacity to consent during the course of the study will be managed as detailed on page 27 of this protocol.

## **STUDY TREATMENT AND REGIMEN**

The study will consist of a Baseline (attack) Visit, and two follow up visits. The baseline visit, which will take place at the earliest timepoint possible following hospital admission at the Nottingham City Hospital, will include a range of investigations, including lung function tests, blood tests and questionnaires.

The second visit will take place approximately two weeks after hospital discharge at the Nottingham Respiratory Research Unit, at which further lung function tests, blood tests and questionnaires will be performed.

The third visit (telephone follow up) will be arranged approximately four weeks after hospital discharge and will consist of questionnaires to determine the degree of symptomatic recovery.

Investigations included in the baseline visit, second visit and third visit (telephone follow up) are listed in figure 1 and table 1. Patients admitted on more than one occasion with an attack will undergo attack visit investigation on each occasion if they consent to this.

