### PRIMARY OBJECTIVE

- To describe the symptom burden, lung function, inflammatory profile, and infection status in patients admitted to hospital with suspected asthma attacks.

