### SECONDARY OBJECTIVES

- Determine the proportion of patients hospitalised with suspected asthma attacks likely due to non-asthma pathology.
- Describe and assess the incidence of extra-pulmonary co-morbidities in patients hospitalised with asthma attacks.
- Assess incidence of risk factors for attacks based on patients' previous history.
- Assess patients' adherence with asthma medications.
- Compare the use of Forced Oscillation Technique (FOT) as a non-effort dependent measure of airway obstruction in suspected severe asthma attacks to a standard measure of airway obstruction Peak Expiratory Flow Rate (PEFR).
- Compare the use of Fractional Exhaled Nitric Oxide (FeNO) as a measure of airway inflammation against sputum and blood eosinophils.
- Describe objective and symptomatic treatment response and recovery from severe asthma attacks following hospital discharge.

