## STUDY DESIGN

### STUDY CONFIGURATION

This is a single centre observational, longitudinal study. The study will aim to recruit 100 patients hospitalised due to a suspected asthma attack. They will be identified from the Respiratory admission units or inpatient wards at the Nottingham City Hospital or the emergency department at Queens Medical Centre.

The initial assessment will take place at the earliest timepoint possible following hospital admission with a suspected asthma attack. A range of investigations, including lung function tests, blood tests, and questionnaires, will be performed. A follow-up visit will be arranged, which will take place approximately two weeks after hospital discharge at the Nottingham Respiratory Research Unit, at which further lung function tests, blood tests and questionnaires will be performed.

A subsequent telephone follow-up visit will be scheduled at around four weeks after hospital discharge, at which additional questionnaires will be performed to determine the degree of symptomatic recovery. A PhD student will perform the majority of study recruitment and study interventions under the fellow's direct supervision.

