## STATISTICS

### Methods

Data analysis will be performed by a PhD student, [name], under the supervision of [name], [name] and [name].

The main outcomes of the exacerbation are descriptive in nature, and no statistical tests are planned. We will, however, compare key findings at exacerbation visits with those undertaken at the follow-up visits, including: Paired tests (paired t-test or McNemar) will be used to examine changes in fractional exhaled nitric oxide (FeNO), parameters derived from Forced Oscillation Technique (FOT), the Acute Asthma Quality of Life Questionnaire (Acute AQLQ), sputum differential cell count, nasal absorption, haematology, and clinical chemistry values.

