## Assessment of safety

An assessment of safety to conduct study procedures will be carried out for each patient prior to recruitment in study and again prior to potential sputum induction. Participants will specifically be asked about the need for further urgent or emergency assessments or treatment for acute asthma at their follow up visit.

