## Procedures for missing, unused and spurious data

Values outside the accepted range will be investigated for accuracy. As the focus of this study is descriptive, complete cases analyses will be the primary method for data analysis.

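### Does the plan need a rule for which attack is analysed when a patient is admitted more than once?

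*Combined protocol and SAP*

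**What the plan says.** Under Study Treatment and Regimen, after setting out one baseline visit and two follow-ups, the protocol adds: "Patients admitted on more than one occasion with an attack will undergo attack visit investigation on each occasion if they consent to this". It does not say there whether the follow-up visits are repeated too. The schedule of assessments (Table 1) has one attack column, one visit at day 14 ± 2 and one telephone contact at day 28 ± 2.

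The objectives are worded per patient. The primary objective describes findings "in patients admitted to hospital with suspected asthma attacks". The first secondary objective is: "Determine the proportion of patients hospitalised with suspected asthma attacks likely due to non-asthma pathology". Study Configuration says: "The study will aim to recruit 100 patients hospitalised due to a suspected asthma attack".

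The Methods paragraph of the Statistics section calls the main outcomes descriptive. It then says that the investigators will "compare key findings at exacerbation visits with those undertaken at the follow-up visits", and that "Paired tests (paired t-test or McNemar) will be used to examine changes" in FeNO, oscillometry, quality of life and laboratory measures. On missing data, "complete cases analyses will be the primary method for data analysis". Participant Duration caps participation at 12 weeks. Under Assessment of Safety: "Participants will specifically be asked about the need for further urgent or emergency assessments or treatment for acute asthma at their follow up visit".

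**The concern.** Attack investigations can repeat within a patient, yet the Statistics section gives no unit of analysis, no index attack and no allowance for within-patient correlation. Its comparison is phrased in terms of visits, while the objectives are phrased in terms of patients. Two analysts could in principle build different denominators.

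Two things would be at stake if attacks were pooled:

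- **Proportions.** Readmitted patients would be counted more than once. If they differ in non-asthma pathology, comorbidity or adherence, the reported share would describe admissions rather than patients. The share with a non-asthma cause matters most, because it carries the study's stated hypothesis.
- **Paired tests.** The paired t-test and McNemar's test assume independent pairs. Two pairs from one patient with positively correlated changes would make the tests reject too often.

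It is also unclear whether a readmission falls inside the 12-week limit or starts a new participation.

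**Working it through.** The plan has no figure of its own to reproduce: it declines a sample size calculation, and 100 is a recruitment target. It also gives no readmission rate, trait rate, correlation or significance level. Those values below are assumptions, including the two-sided 5% level.

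**1. What the text implies.** The objectives and target count patients. Table 1 lays out one attack visit with its own follow-ups. Medical history, demographics and the comorbidity questionnaires sit in that single attack column, and summarising them per patient is the natural reading. The plural visits in the Methods paragraph can equally mean one visit for each of many patients. No sentence asks for attacks to be pooled.

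**2. Proportions, if attacks were pooled anyway.** Let p be the share of patients with two attacks, and let the trait rate be t in them and 30% in the others.

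- Per patient: (1 − p) × 0.30 + p × t
- Per attack: [(1 − p) × 0.30 + 2p × t] / (1 + p)

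For p = 10% and t = 60%, the per-patient value is 0.27 + 0.06 = 33.0% and the per-attack value is (0.27 + 0.12)/1.10 = 35.5%.

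| p | t | Per patient | Per attack | Shift (points) |
|---|---|---|---|---|
| 5% | 60% | 31.5% | 32.9% | 1.4 |
| 10% | 60% | 33.0% | 35.5% | 2.5 |
| 20% | 60% | 36.0% | 40.0% | 4.0 |
| 5% | 45% | 30.8% | 31.4% | 0.7 |
| 10% | 45% | 31.5% | 32.7% | 1.2 |
| 20% | 45% | 33.0% | 35.0% | 2.0 |
| any | 30% | 30.0% | 30.0% | 0 |

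For scale, the 95% half-width at 30% with 100 patients is 1.96 × √(0.30 × 0.70/100) = 9.0 points.

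The same question can be set up from the readmission side. Take a true share of 20% and a 10% repeat rate in patients without the trait. Repeat rates of 10%, 20%, 30% and 50% in those with it give pooled shares of 20.0%, 21.4%, 22.8% and 25.4%. A repeat rate of 10% with the trait and 30% without gives 17.5%. The half-width at 20% is 7.8 points.

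**3. Paired tests, only if a repeat attack also has a recovery visit.** With cluster sizes m of 1 or 2, the design effect is 1 + ρ × (Σm²/Σm − 1), where ρ is the within-patient correlation of change scores. For 100 patients the bracket is 115/105 − 1 = 0.0952 at p = 5%, 130/110 − 1 = 0.1818 at 10% and 160/120 − 1 = 0.3333 at 20%. The true level is 2 × P(Z > 1.96/√design effect).

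| ρ | p = 5% | p = 10% | p = 20% |
|---|---|---|---|
| 0.1 | 5.1% | 5.2% | 5.4% |
| 0.3 | 5.3% | 5.6% | 6.2% |
| 0.5 | 5.5% | 6.1% | 7.0% |
| 0.8 | 5.9% | 6.7% | 8.2% |

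At p = 30% and ρ = 0.8 the level reaches 9.4%. Stable patient characteristics cancel in a change score, so low correlations are plausible. A correlation of 0.5 would arise if two attacks shared one recovery visit (equal, independent visit errors). That normally requires readmission before the second visit, so within about 16 days of the first discharge, and the 5% to 20% shares would then be too high.

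**4. The reading closest to the text.** A repeat admission is promised the attack investigation only. Without a recovery visit it forms no pair, drops out under complete-case analysis, and leaves the paired tests as they were.

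**The case for a change.** The strongest counter-argument is that a descriptive study's product is its proportions, and a proportion needs a defined denominator. Calling the study hypothesis-generating does not remove that need. The Statistics section is where the rule belongs, and it is silent. Stating the rule before the data are seen would also prevent a choice of attack made after seeing results, at the cost of a few sentences.

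The omission is real, and Figure 1, which I have not seen, is unlikely to contain an analysis rule, though it may show whether follow-up repeats. But the silence leaves only one reading that fits objectives and a target both counted in patients. Pooling would depart from those words. Using one record per patient needs no new data or method, and repeat attacks can still be described separately. Whether follow-up visits repeat, and how a readmission sits with the 12-week limit, are questions of conduct and do not change the per-patient result. The question about further urgent care at follow-up already gives an approximate marker of early relapse, although it does not ask specifically about readmission.

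**Conclusion.** No change follows. This is a gap in written detail that an analyst would fill sensibly from the objectives, and the per-patient results would stand.

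The harm needs a pooling decision that the plan does not make, and then further conditions. The proportions shift only if readmitted patients differ. Under the contrasts tabulated above, the shift is 0.7 to 4.0 points, against a half-width of about 9 points at 30%. The most extreme alternative tried moves a 20% share by 5.4 points. The tests are affected only if repeat attacks acquire their own or a shared recovery visit and changes correlate within patient. For 5% to 20% repeaters the level is then 5.1% to 8.2%, and it is 9.4% at 30% repeaters with a correlation of 0.8. These are supplementary comparisons in a descriptive study.

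The repeat rates, trait rates, correlations and 5% level are all assumed. The conclusion that no change is needed rests on the per-patient wording, not on those values. It would weaken if the investigators intended to report attacks, rather than patients, as the unit.

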## **Study Assessments Algorithm.**

[figure not shown]

Figure 1: Study assessments algorithm.

Definition of abbreviations: WCC = white cell count; FeNO = fractional exhaled nitric oxide; FOT = forced oscillation technique; PCR = polymerase chain reaction; MC+S = microscopy culture + sensitivity; SNOT = Sino-nasal outcome test; GERDQ = gastroesophageal reflux disease questionnaire; VCD = vocal cord dysfunction; HADS = hospital anxiety and depression scale; BMI = body mass index; CRP = c-reactive protein; PAAP = Personalised Asthma Action Plan; MARS = medication adherence report scale; AQLQ = asthma quality of life questionnaire.

### Schedule of study assessments.

Visit	Baseline visit	Second visit	Telephone visit
Time	Attack	Day 14 +/-2	Day 28 +/-2
Investigations Performed			
Informed Consent	X		
Medical History	X		
Concomitant Medications	X		
Demographic Data	X		
Sino-nasal Outcome Test	X		
Gastroesophageal Reflux Disease Questionnaire	X		
Pittsburgh Vocal Cord Dysfunction Index	X		
Nijmegen	X		
Hospital Anxiety and Depression Scale	X		
Medication Adherence Report Scale	X		
Inhaler Technique check	X		
Acute Asthma Quality of Life Questionnaire	X	X	X
Spirometry and PEFR	X	X	
Fractional Exhaled Nitric Oxide (FeNO)	X	X	
Forced Oscillation Technique (FOT)	X	X	
Clinical Chemistry (C- Reactive Protein)	X	X	
Sputum (induced or spontaneous) for differential cell count, supernatant storage and microbiological assessment	X	X	
Blood White Cell Count Differential	X	X	
Vitamin D	X		
Viral PCR: Throat swab.	X		
Nasal lavage	X		
Nasosorption Sample	X	X	
Nasal Epithelium Samples for Genetic Analysis (optional)	X	X	

Table 1: Schedule of study assessments.

## Study Assessments

### Medical History, Demographics and Concomitant Medications

Medical history will include clinically significant diseases and prior surgeries and smoking history. A specific respiratory history will also be recorded. Demographic data will include age, sex and self-reported race/ethnicity. Medication use will also be collected.

### Height, Weight and Blood Pressure

Height, weight and blood pressure measurements will be obtained from medical record.

### Sino-nasal Outcome Test

The incidence of upper airway symptoms will be assessed using Sino-nasal Outcome Test (SNOT).

### Gastroesophageal Reflux Disease questionnaire.

The incidence of Gastroesophageal Reflux Disease will be assessed using GERDQ questionnaire.

### Pittsburgh Vocal Cord Dysfunction Index

The incidence of vocal cord dysfunction will be assessed using Pittsburgh Vocal Cord Dysfunction (VCD) Index

### Nijmegen Questionnaire.

The incidence of dysfunctional breathing will be assessed using Nijmegen dysfunctional questionnaire.

### Hospital Anxiety and Depression Scale

The incidence of anxiety and depression will be assessed using Hospital Anxiety and Depression Scale (HADS).

### Medication Adherence Report Scale

Participants' adherence to medication will be assessed using the Medication Adherence Report Scale (MARS).

### Acute Asthma Quality of Life Questionnaire

The impact of acute asthma on quality of life will be assessed using Acute Asthma Quality of Life Questionnaire at baseline and follow up.

### **Fractional Exhaled Nitric Oxide (FeNO)**

FeNO will be measured using a standard device (NIOXX Vero®) in accordance with the manufacturer's guidelines. The same type of device will be used at each visit. FeNO should be performed prior to any other respiratory assessment if possible.

### **Forced Oscillation Technique (FOT)**

FOT is a non-invasive method that evaluates resistance and reactance in the respiratory system during tidal breathing. It should be performed after FeNO, but prior to Spirometry and will be conducted according to a study SOP.

### **Spirometry**

Spirometry will be conducted according to a study SOP. The Global Lung Function (GLI) 2012 equations will be used. Reversibility testing will not be routinely performed. Thus, asthma medications will not normally be withheld for study visits and patients should take their inhalers as usual. The same type of device will be used at each visit.

### **Induced and Spontaneous Sputum**

Sputum induction will be performed according to an SOP, which includes measures to protect the safety of participants. These consist of pre-treatment with Salbutamol, a short acting bronchodilator, stipulated levels of lung function in order to perform the test and stopping criteria. If the participant is unable to undergo the procedure, due to safety reasons, they will be asked to produce a spontaneous sputum sample. Sputum samples will be collected for a differential cell count, bacterial culture and sensitivity and storage for future research. Procedures for sampling and processing will be detailed in a study SOP.

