## **Safety endpoints**

As this is an observational study, there are no defined safety endpoints, although investigations at the time of exacerbation will not be performed if there are safety concerns.

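### The paired sputum comparison takes no account of collection method, which depends on lung function and so may differ between the attack and recovery samples of the same patient

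*Combined protocol and SAP*

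**What the plan says.** The section on Induced and Spontaneous Sputum refers induction to an SOP whose safeguards include "stipulated levels of lung function in order to perform the test and stopping criteria". The level itself is not given. The fallback is: "If the participant is unable to undergo the procedure, due to safety reasons, they will be asked to produce a spontaneous sputum sample". The rule is not tied to a visit, and Assessment of Safety provides for a safety check at recruitment and "again prior to potential sputum induction".

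Table 1 has a single row, "Sputum (induced or spontaneous) for differential cell count, supernatant storage and microbiological assessment", marked at the attack visit and at the second visit (Day 14 +/-2).

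The statistical Methods plan paired tests (paired t-test or McNemar) of change between the exacerbation and follow-up visits. The variables listed include "sputum differential cell count, nasal absorption, haematology, and clinical chemistry values". On missing data, the plan says that "complete cases analyses will be the primary method for data analysis".

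Neither statistical section mentions how the sputum was obtained. For FeNO and spirometry, by contrast, the Study Assessments section keeps the type of device constant across visits.

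**The concern.** The collection method is not assigned at random with respect to the outcome. It follows lung function, which is itself expected to change between the two visits. A patient below the induction limit at the attack and above it at the second visit changes method because of recovery. If the two methods yield different cell fractions for any reason unrelated to disease, that difference enters the paired change with the same timing as the recovery the study wants to describe. It could imitate a change or mask one.

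Sputum inflammatory cell count at attack and recovery is one of the listed outcome measures, all of which the protocol treats as equally important. It bears on the inflammatory-profile objective and on the recovery objective. Sputum eosinophils are also a comparator for FeNO. If sample type is not available as an analysis variable, mixed pairs cannot be identified afterwards.

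**Working it through.** The plan has no figure to reproduce. It gives no sample size calculation, alpha, effect size or standard deviation, and 100 is a recruitment target.

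**Inputs from the documents.** Method depends on a lung-function limit; either method is allowed at both visits; the differential count is tested as paired data on complete cases; at most 100 patients contribute a pair, leaving aside repeat admissions.

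**Inputs not in the documents (assumed).** The share of pairs that switch method, the size of any method effect, the number of usable pairs, and a two-sided 5% level.

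**Step 1: mean bias.** Let *a* and *r* be the shares of pairs with a spontaneous sample at attack and at recovery, and *d* the induced-minus-spontaneous difference, taken as constant across patients. The bias in the mean change (recovery minus attack) is

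bias = (a − r) × d.

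Only the net switch counts:
- a = 30%, r = 0%: bias = 0.30 × d
- a = 30%, r = 10%: bias = 0.20 × d
- a = 30%, r = 30%: bias = 0

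The bias is also zero at any *a* and *r* if d = 0.

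**Step 2: effect on the paired test when disease does not change.** Take the one-way case, in which a share *s* goes from spontaneous to induced and none go the other way. Express the method effect *m* in SDs of the paired difference. Then

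shift = s × m, SD = √(1 + s(1 − s)m²), λ = shift × √n / SD,

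and by normal approximation the false-positive rate is Φ(λ − 1.96) + Φ(−λ − 1.96).

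Example: n = 100, s = 0.20, m = 0.5. Shift = 0.10; SD = √(1 + 0.16 × 0.25) = √1.04 = 1.020; λ = 0.10 × 10 / 1.020 = 0.98; rate = 16.5%.

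| s | m | shift (SD) | rate, 40 pairs | rate, 100 pairs |
|---|---|---|---|---|
| 10% | 0.25 | 0.025 | 5.3% | 5.7% |
| 20% | 0.5 | 0.10 | 9.5% | 16.5% |
| 30% | 0.5 | 0.15 | 15.2% | 31.0% |
| 50% | 1.0 | 0.50 | 80.7% | 99.4% |

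The first row is negligible and the last is dominant. Nothing in the documents says which row is nearest to this study.

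**Step 3: price of using same-method pairs only.** Dropping a share *s* of pairs multiplies the standard error by 1/√(1 − s), if the SD is unchanged: 1.12 at 20%, 1.29 at 40%, 1.58 at 60%.

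**The case against.** A reader might infer that the rule sends the most obstructed patients to spontaneous sputum at the attack and to induced sputum at recovery. The documents do not support that as a statement of fact. The same rule and the same safety check apply at both visits, the limit is in an SOP that is not shown, and the background says that recovery times vary. Some patients may be below the limit at both visits and others above it at both, and neither group switches. The protocol itself expects a significant proportion of admissions to have a cause other than asthma.

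There is also a second route. The Safety Endpoints section says that "investigations at the time of exacerbation will not be performed if there are safety concerns", and the fallback only asks for a spontaneous sample. Some of the most obstructed patients may therefore have no attack sample and leave the complete-case analysis. That is selection, not a change of method, and it lowers the number of mixed pairs.

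No passage says that the two methods give different cell fractions, so the method effect is an assumption. The CRF, the SOP and the laboratory manual are not available, and sample type may already be recorded in one of them. The study is hypothesis-generating, and this is one of several secondary paired comparisons.

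All of this stands, and it limits the claim to a possible bias of unknown size. It does not supply the missing analysis rule: the statistical sections would pool same-method and mixed pairs without distinction.

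**Conclusion.** The gap is real and worth closing. As written, the plan lets method vary within a patient in a way that depends on lung function, then tests the paired change as if method were constant. For any patient who crosses the limit, the two sources of change are merged. Switching is more likely from spontaneous at attack to induced at recovery than the reverse. That direction is an expectation based on lung function being worse at the attack, not something the documents establish.

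The size is the net switch times the method difference, from zero to material. The rates above show the sensitivity of the test under assumed inputs; they are not estimates for this study. It would be tempting to quote a fixed bias of several percentage points in a cell fraction, but that would require a switching share and a method difference that the documents do not give, and it would rule out a null net effect without grounds.

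The point is confined to the sputum differential count. Extending it to culture or stored supernatant is not supported: neither is among the variables listed for paired testing, and supernatant is kept for future work.

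**What to change.** - Record sample type (induced, spontaneous or none) at each visit as an analysis variable, if the CRF does not already do so.
- In the statistical Methods, keep the comparison on all pairs, and report the paired change separately for induced-induced, spontaneous-spontaneous and mixed pairs, giving the direction of the mixed ones.
- Pre-specify a sensitivity analysis restricted to same-method pairs, and state that a change seen only in mixed pairs will not be interpreted as recovery.
- Report how many patients have no sputum pair.
- Present the attack sputum profile by sample type.

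The cost is one CRF item per sample and one further table. The strata will be small, and the same-method analysis loses precision as shown in Step 3. Same-method pairs are also selected on lung function: induced-induced pairs lean towards patients less obstructed at the attack, spontaneous-spontaneous pairs towards those who stayed below the limit, and patients who recovered across the limit are left out. For that reason the same-method result should accompany the all-pairs result and not replace it. The induction safety limits are not affected.
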